8.6. Data Management

[figure not shown]
Harvard Pilgrim Health Care Institute (HPHCI), located in Boston, Massachusetts, will serve as the coordinating center for the proposed study. HPHCI staff or contractors will be responsible for writing and distributing Statistical Analysis System (SAS) programs that can be used to evaluate data from the administrative claims databases at participating Data Partners. The distributed network will leverage the SCDM (Sentinel 2021; Curtis 2012) which allows Data Partners to maintain physical and operational control of their data while allowing use of their data to meet the study needs. The HPHCI will maintain a secure distributed querying web-based portal to enable secure distribution of analytic queries, data transfer and document storage. The system will meet all required State and Federal security guidelines for health data (eg, Federal Information Security Management Act [FISMA], HIPAA) and will be specifically FISMA-compliant for FISMA security controls as specified in the National Institute of Standards and Technology (NIST) Special Publication 800-53 (NIST and Joint Task Force Transformation Initiative 2020).

HPHCI brings expertise in conducting multi-site evaluations using disparate electronic healthcare data systems, including extensive work with the Health Care Systems Research Network, the Vaccine Safety Datalink, FDA Sentinel, the National Institutes of Health Care Systems Research Collaboratory, Innovation in Medical Elements Development [IMEDS], the Biologics and Biosimilars Collective Intelligence Consortium, and PCORnet. The HPHCI Coordinating Center has expertise in conducting large-scale multi-site studies using various distributed analytic approaches, form common data models and analytics to common protocols implemented locally, and is well positioned to implement the planned study. In collaboration with RTI Health Solutions, HPHCI will oversee all project activities, including scientific leadership, management of the

partnership, coordination of activities with the Data Partners and other participants, oversight of the project plan and budgets, establishment of secure infrastructure used for collaboration, and training related to use of the SCDM and associated querying tools. The Data Partners will establish and maintain the administrative, hardware, and software capabilities and capacity to respond to data requests in a timely manner. They will also provide data science support with epidemiologic review.

Figure 3 describes the general workflow for the final analysis. Based on the study design developed by the study team, the study coordinating center first submits a computer program designed to meet the needs of the study through a secure portal. Next, the participating Data Partners receive and run the computer program behind their firewalls, using data that is formatted to the SCDM. Following this, the Data Partners review their results and return them to the study coordinating center through a secure portal. Finally, the study coordinating center reviews the results returned by the Data Partners, aggregates the data across the sites and then transfers the aggregated results back to the study team.

Figure 3: Workflow

8.7. Data Analysis

Statistical analyses of each Data Partner's aggregated data will be performed by the coordinating center and will align with analyses described in this study protocol. A general description of the planned statistical methods to be used to analyze the data collected in this study is presented in the following subsections. Additional details will be provided in the SAP. A summary of planned analyses is provided in Table 4.

Table 4: Summary of Planned Analyses

Analysis	Study design for Acute AESIs	Study design for Non-acute AESIs	Risk period Definition of Risk Period	Notes on main purpose of analysis/difference from primary analysis
Primary	SCRI	Cohort: exposed (Ad26.COV2.S) vs. active comparator (BNT162b2)	Disease-specific risk period	NA
Stratified analysis (by comorbidities and by age)	SCRI	Cohort: exposed (Ad26.COV2.S) vs. active comparator (BNT162b2)	Disease-specific risk period	Subgroup analysis
Sensitivity	SCRI	Cohort: exposed (Ad26.COV2.S) vs. active comparator	Extended disease- specific risk period	Incorporates use of alternative disease risk periods
Sensitivity	NA	Cohort: exposed (Ad26.COV2.S) vs. active comparator (BNT162b2)	Disease-specific risk period	Alternate comparison of Ad26.COV2.S to first or second dose of BNT162b2
Sensitivity	Cohort: exposed (Ad26.COV2.S) vs. active comparator (BNT162b2)	NA	Disease-specific risk period	Incorporates use of alternate study design
Secondary	Descriptive analysis of Ad26.COV2.S- exposed individuals in the cohort who have received a second dose of Ad26.COV2.S	Descriptive analysis of Ad26.COV2.S-exposed individuals in the cohort who have received a second dose of Ad26.COV2.S	Disease-specific risk period	Describe counts for and characteristics of individuals receiving 2 nd dose of Ad26.COV2.S

AESI = adverse event of special interest; SCRI = self-controlled risk interval; NA = not applicable.

Note: Acute AESIs are events expected to occur within 60 days of vaccination.

8.7.1. Main Summary Measures

The primary analysis will compare the incidence rates of each AESI between risk period and control period (SCRI for acute events) for Ad26.COV2.S exposed individuals, or between Ad26.COV2.S exposed individuals and BNT162b2 exposed individuals (cohort design with active comparator for non-acute events). All analyses will be conducted separately, with PS adjustment, within each data source and pooled across data sources using a random-effects model or another appropriate method to be specified in the SAP.

8.7.1.1. Self-controlled Risk Interval Design

The incidence rate ratio comparing AESI incidence during the risk and control periods will be estimated using conditional Poisson regression models (Whitaker 2006).

8.7.1.2. Cohort Design With Active Comparator

Incidence rates for each AESI will be calculated by dividing the number of cases by the follow-up person-time in each of the matched exposure groups. Incidence rate ratios and 95% CIs will be estimated with Poisson regression modeling or another appropriate method to be defined in the SAP. The risk difference will be computed as the difference between the incidence rate in the exposed cohort and the incidence rate in the comparator cohort.

Daily cumulative incidence will be estimated in each exposure group as 1 minus the Kaplan Meier estimate, and the cumulative incidence curves of the occurrence of AESI over time in the risk periods will be plotted in the matched cohorts to visualize time trends with days since the reference date as the time scale.

The percentage of outcomes that were preceded by a documented SARS-CoV-2 infection (COVID-19 diagnosis code or SARS-CoV-2 positive laboratory test result) after the first dose of either the Ad26.COV2.S or comparator BNT162b2 vaccine will be reported.

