Follow-up will begin on or the day after the reference date; follow-up time will end at the earliest of the following: date of first diagnosis of AESI, death, disenrollment from the health plan, administrative end of the study (eg, end of available data), end of duration of the risk period specific to the AESI (up to 1 year after the reference date), date of any COVID-19 vaccine that is not the index vaccine, or date of receipt of

an additional or booster dose beyond the authorized primary series (ie, a second dose of COVID-19 in the Ad26.COV2.S cohort or a third dose of COVID-19 vaccine in the BNT162b2 cohort).

Feasibility assessment (monitoring phase)

At study initiation, counts of Ad26.COV2.S vaccine exposures and any mRNA vaccine exposures, including primary vaccination series, baseline characteristics, and the number of AESIs, will be monitored from each database to confirm the feasibility of implementing the planned final analysis in the available data sources for specific AESIs. The crude incidence rate for each AESI in the risk intervals following vaccination for first-dose Ad26.COV2.S vaccinees and first dose of any mRNA vaccinees will be calculated for each individual AESI after excluding individuals with prior evidence of that AESI before cohort entry in specified time windows.

The observation period for the monitoring analysis will start on the launch date of Ad26.COV2.S in the US (27 February 2021).

Setting and Study Population

For the SCRI design, eligibility criteria will be applied separately for analysis of each AESI. Individuals over the age of 18 years at the reference date will be included if they have received a first dose of Ad26.COV2.S vaccine during the study period, experienced the AESI during the risk or control period, and have at least 1 year of continuous medical and prescription drug coverage prior to the date of vaccination until the end of the AESI-specific control interval.

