8.3.5.2. Cohort Design with Concurrent Active Comparator

Follow-up time for the primary objective evaluating the first dose of Ad26.COV2.S or the primary series of BNT162b2 will start on or the day after the reference date (depending on the specific AESI risk window) and will continue until the earliest of the following:

- date of first diagnosis of the AESI
- end of the duration of the disease-specific risk period (specified in Table 1; up to 1 year after the reference date)
- disenrollment from the health plan
- administrative end of study (eg, end of available data)
- death
- date of any COVID-19 vaccine that is a different brand than the index vaccine
- date of receipt of an additional or booster dose beyond the authorized primary series (ie, a second dose of COVID-19 vaccine in the Ad26.COV2.S cohort or a third dose of COVID-19 vaccine in the BNT162b2 cohort)

The authorized primary series of BNT162b2 consist of 2 doses, spaced 21 days apart. If the AESI-specific risk period after dose 1 of BNT162b2 ends before a second dose is received, follow-up will end at the end of the dose 1 disease-specific risk period. However, a second dose of BNT162b2 may be received during the dose 1 disease-specific risk periods of some AESI. If a second dose is received before the end of the AESI-specific risk period, the risk periods of dose 1 and dose 2 will be concatenated into a single risk period, and follow-up will end after the duration of the disease-specific risk period following dose 2. To address differential lengths of follow-up time between the exposed and comparator cohorts that will arise from including second doses of BNT162b2 in the comparator cohort, modifications of this criteria will be evaluated in sensitivity analyses (Section 8.7.5).

Note that follow-up time will not be censored if a diagnosis of COVID-19 occurs after the initial vaccine dose. Only severe COVID-19 that arises to medical attention will be captured given the nature of the available data. This information will be captured and used in descriptive analyses.

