8.7.3. Stratified Analyses

Analyses within the primary study designs (cohort design with active comparator for non-acute events and SCRI design for acute events) will be stratified by the following clinically relevant subgroups:

- select comorbidities (by the presence or absence of comorbidity)
- frailty
- receipt of other vaccinations concurrently with Ad26.COV2.S
- age ([18-39]; [40-59]; [60-79], [80+])
- prior history of thrombotic events and/or thrombocytopenia
- prior history (ever) of specific event more than a year before start of follow-up
- prior history of COVID-19 infection

For the cohort design with active comparator, the original study population before matching will be divided into these subgroups and the PS matching will be repeated in each of the subgroups to create matched exposed and comparator cohorts within the subgroups. The balance of individual characteristics by exposure group will be re-evaluated within each subgroup, and subgroup-specific incidence rate and incidence rate ratios with 95% CIs will be estimated.

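### The cumulative incidence curves treat death as censoring, so those for the four 365-day AESIs modestly overstate the actual probability of the event

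*Protocol*

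**What the plan says.** Protocol section 8.7.1.2 fixes the estimator for the cohort design: "Daily cumulative incidence will be estimated in each exposure group as 1 minus the Kaplan Meier estimate". The curves have a descriptive purpose; they "will be plotted in the matched cohorts to visualize time trends with days since the reference date as the time scale".

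The abstract gives the exit rule: "follow-up time will end at the earliest of the following: date of first diagnosis of AESI, death, disenrollment from the health plan", followed by administrative and vaccination-related exits. Section 8.3.5.2 repeats it. Follow-up "will continue until the earliest of the following", and the list puts death beside disenrollment, end of data, a switch of brand and the "date of receipt of an additional or booster dose beyond the authorized primary series". Neither section sets death apart from the other exits or names a competing-risk method.

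The comparative measures in section 8.7.1.2 are of another kind. "Incidence rate ratios and 95% CIs will be estimated with Poisson regression modeling or another appropriate method to be defined in the SAP". What the section calls the risk difference is one cohort's incidence rate subtracted from the other's. Both measures come from events and person-time.

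The cohort design is primary for the four AESIs with a 365-day window: autoimmune thyroiditis, acute aseptic arthritis, multiple sclerosis and Type 1 diabetes mellitus. It is a sensitivity analysis for the acute AESIs, whose windows run from 2 to 42 days.

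**The concern.** Cumulative incidence is normally read as the share of vaccinees who have the event by a given day. One minus Kaplan-Meier estimates that share only if everyone who leaves follow-up could still have the event afterwards. This can be argued for someone who changes insurer, but not for someone who has died. With death censored, the curve answers a hypothetical question, namely the risk if nobody died, and the protocol does not say that this is the quantity it wants.

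The study has no upper age limit, and the four non-acute AESIs are followed for up to a year, so some deaths will occur in the window. Because the risk difference is defined on rates, these curves are the only planned estimates of AESI occurrence on the probability scale. A reader who takes an absolute risk from them will take one that is somewhat too high. The protocol fixes this estimator outright, whereas it leaves the rate-ratio method open to the SAP.

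**Working it through.** **The plan's own figures.** The protocol gives no cumulative incidence and no mortality, so there is no stated figure on this point to reproduce. The nearest figure for the cohort design is the precision example in section 8.5.2 (100,000 exposed, 400,000 comparators, 60 days, 50 per 100,000 person-years, true relative risk 1.0).

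- Expected exposed cases: 100,000 × 60/365 × 50/100,000 = 8.22. Expected comparator cases: four times that, 32.88.
- SE of the log ratio: √(1/8.22 + 1/32.88) = 0.390.
- Probability that the upper limit is below 3.0: Φ(ln 3/0.390 − 1.96) = 0.804, against the stated 0.805.

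This confirms that the precision planning rests on person-time counts and does not involve Kaplan-Meier.

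**Inputs for the curves.**

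- AESI rate *l*: Table 1 upper ends for three of the 365-day AESIs, namely 29 (multiple sclerosis), 97 (autoimmune thyroiditis) and 382 (Type 1 diabetes mellitus) per 100,000 person-years.
- Death hazard *m*: an assumption, varied from 0.01 to 0.20 per year.
- Window *T* in years.

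**Formulas, constant hazards.**

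- One minus Kaplan-Meier, death censored: 1 − exp(−*lT*).
- Aalen-Johansen, death competing: *l*/(*l*+*m*) × [1 − exp(−(*l*+*m*)*T*)].
- For a rare AESI, their ratio is close to *mT*/(1 − exp(−*mT*)), which does not depend on *l*.

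**365-day window, *l* = 97 per 100,000 person-years** (results per 100,000 people):

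| Assumed death hazard per year | 1 − KM | Aalen-Johansen | Relative excess |
|---|---|---|---|
| 0.01 | 96.95 | 96.47 | 0.5% |
| 0.04 | 96.95 | 95.04 | 2.0% |
| 0.05 | 96.95 | 94.57 | 2.5% |
| 0.10 | 96.95 | 92.26 | 5.1% |
| 0.20 | 96.95 | 87.87 | 10.3% |

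The 0.04 row is 0.00097/0.04097 × (1 − exp(−0.04097)) = 0.0009504. The rare-event formula agrees: 0.04/(1 − exp(−0.04)) = 1.020. At 29 and 382 per 100,000 the relative excess is practically the same.

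**Simulation check.** Four million simulated people with *l* = 382 per 100,000, *m* = 0.10 and independent censoring gave 0.00384 for 1 − KM and 0.00366 for Aalen-Johansen, a ratio of 1.050.

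**Short windows.** Over death hazards of 0.01 to 0.20 per year, the excess is 0.04% to 0.77% at 28 days and 0.06% to 1.16% at 42 days. A comparator's window lengthens when the second dose falls inside it. For a dose on schedule at day 21 it is 21 + 42 = 63 days, and *mT*/2 at *m* = 0.10 is 0.10 × (63/365)/2 = 0.9%, still small.

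**Comparison between arms, 365 days.** With equal death hazards of 0.10 and a true ratio of 1.2, the ratio of the two curves is 1.1999 by either method. With no true difference and death hazards of 0.12 against 0.10, the Aalen-Johansen ratio is 0.990, and with 0.15 against 0.10 it is 0.976. The Kaplan-Meier ratio stays at 1.0 in both cases.

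**Scale against sampling error.** With 100,000 exposed followed for the full year, 97 expected events give a relative standard error of 1/√97, about 10%. Real follow-up is shorter because of the other exits, so the true figure is larger.

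**The case against.** The best defence is that nothing comparative depends on these curves. The rate ratio and rate difference end person-time at death, which is standard, and the curves are there to show time trends. One minus Kaplan-Meier also has a valid meaning as the risk with death removed, if censoring is independent, and it matches the scale of the rate analysis. Within any plausible mortality for a whole adult cohort, the excess is below the sampling error. All of this stands. It limits the point to a descriptive output and to the label it carries, but it does not make the label right, since the protocol never states the hypothetical quantity.

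A reader might infer more than the documents support:

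- *That the risk differences or rate ratios are biased.* They are not, because they do not use Kaplan-Meier.
- *That the worst error will appear in the 80+ stratum.* The gap does grow with mortality, but section 8.7.3 lists only rates and rate ratios for the subgroups. No curve by age is planned.
- *That the comparison of arms is distorted.* This would need different mortality in the matched cohorts. The documents give no evidence of that, and the propensity score includes age, comorbidities and frailty.
- *That Aalen-Johansen removes the bias at no cost.* It deals with recorded deaths only. Independence must still be assumed for disenrollment, brand switch and booster. The data-source descriptions in section 8.4 do not say how completely death is captured, and a death that appears only as disenrollment would remain censored.

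**Conclusion.** The point holds as a minor one. Section 8.7.1.2 gives the name cumulative incidence to an estimator that, with death as an ordinary exit, lies above the actual probability of the AESI as soon as anyone at risk dies. That death is treated as censoring follows from reading sections 8.7.1.2 and 8.3.5.2 together; no single sentence says it.

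For the four 365-day AESIs the relative overstatement is about 0.5%, 2% and 5% at death hazards of 0.01, 0.04 and 0.10 per year. For windows of 42 days or less it is at most about 1.2%, even at 0.20 per year. These sizes rest on assumed mortality and constant hazards. The direction does not depend on either. No incidence rate ratio, rate difference or subgroup result changes.

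**What to change.** In section 8.7.1.2, replace one minus Kaplan-Meier by the Aalen-Johansen cumulative incidence with death as a competing event, at least for the four 365-day AESIs. Keep disenrollment, brand switch, additional or booster dose and end of data as censoring. Add one sentence saying that the curve estimates the probability of the AESI in the presence of death. Carry the same wording into the SAP.

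The cost is small but not nil. Results are aggregated within each Data Partner before they are returned, so the distributed programs must output deaths by day and exposure group alongside events and numbers at risk. The report should state how deaths are identified in each data source, because the correction works only for deaths that are recorded.

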8.7.2. Main Statistical Methods

8.7.2.1. Propensity Score Matching

For the cohort designs, matching on calendar time at vaccination (within 2 weeks) and PS will be used to ensure comparability between individuals exposed to Ad26.COV2.S versus BNT162b2. The PS is the predicted probability of an individual being classified in the exposed cohort versus the comparator cohort, given a set of observed covariates. Propensity scores will be estimated with multivariable logistic regression models with Ad26.COV2.S exposure as the dependent variable and baseline covariates as the independent variables. The baseline covariates used to fit the PS model will be the individual characteristics described in Section 8.3.2 and indicators for occurrence of AESI in the disease-washout period described in Section 8.3.4.2.

This large-scale empirical adjustment strategy should address expected confounders that are recorded in the databases, including demographics and comorbidities associated with AESIs. The study will be subject to the limitation that some confounders may be unmeasured or inadequately represented in claims data, including lifestyle behaviors, such as diet and exercise.

8.7.2.2. Demographic and Baseline Characteristics

For the cohort design, disposition will be summarized by cohort and by data sources. Demographic and baseline characteristics of the individuals at the reference date will be described in the matched analytic cohort. For continuous/ordinal variables the number of observations, mean, standard deviation, minimum, and maximum will be described. For categorical variables, the number and percent per category will be summarized. Balance of characteristics between the exposure groups before and after PS matching will be evaluated with absolute standardized differences.

8.7.3. Stratified Analyses

Analyses within the primary study designs (cohort design with active comparator for non-acute events and SCRI design for acute events) will be stratified by the following clinically relevant subgroups:

- select comorbidities (by the presence or absence of comorbidity)
- frailty
- receipt of other vaccinations concurrently with Ad26.COV2.S
- age ([18-39]; [40-59]; [60-79], [80+])
- prior history of thrombotic events and/or thrombocytopenia
- prior history (ever) of specific event more than a year before start of follow-up
- prior history of COVID-19 infection

For the cohort design with active comparator, the original study population before matching will be divided into these subgroups and the PS matching will be repeated in each of the subgroups to create matched exposed and comparator cohorts within the subgroups. The balance of individual characteristics by exposure group will be re-evaluated within each subgroup, and subgroup-specific incidence rate and incidence rate ratios with 95% CIs will be estimated.

8.7.4. Missing Values

Further details of the analysis, including handling of missing data will be described in the SAP.

8.7.5. Sensitivity Analyses

8.7.5.1. Extended Disease-specific Risk Periods

Sensitivity analyses will be performed to assess the risk of AESI within extended disease-specific risk periods for events for which the risk interval is not well known or not currently documented in the vaccine safety literature. These extended disease-specific risk periods will be further described in the SAP.

8.7.5.2. Alternate Follow-up Criteria for Active Comparative Design Based on BNT162b2 Dose (for Non-acute Events)

As described in Section 8.3.5.1, for the primary analysis of non-acute events evaluated using a cohort design, if the disease-specific risk period after dose 1 of the comparator vaccine (BNT162b2) overlaps with the receipt of dose 2, the risk periods for dose 1 and dose 2 will be concatenated together into a single risk period. Sensitivity analyses will be conducted for non-acute events using a cohort design with the active comparator after receiving only a single dose (Figure 4) or after receiving both doses (Figure 5) of the comparator vaccine. Note that sensitivity analysis with the active comparator after receiving only a single dose will be performed only for AESI with risk periods of 21 days or longer (where overlap of the dose 1 risk period with dose 2 of BNT162b2 is expected), as this sensitivity analysis will be identical to the primary analysis if the dose 1 and dose 2 risk periods do not overlap.

exposed cohort: receives only

1 dose

[figure not shown]
T = 0;Vaccine dose Vaccine dose 1 receipt 2 receipt 1-year minimum continuous health plan enrollment: Inclusion/exclusion criteria Risk window assessment window Baseline characteristics Comparator assessment window BNT162b2 exposed cohort: receives 2 doses If vaccine dose 2 is received during the outcome-specific risk period after dose 1, the risk period is censored on the date of dose 2. T = 0: Vaccine dose 1 receipt 1-year minimum continuous health plan enrollment: Inclusion/exclusion criteria Risk window assessment window Baseline characteristics Comparator assessment window BNT162b2

If vaccine dose 2 is not received, the outcome-specific

risk window extends the full length from dose 1.

Cohort Study Design for Sensitivity Analysis After Only a Single Dose of BNT162b2 Figure 4:

Figure 5: Cohort Study Design for Sensitivity Analysis After Both Doses of BNT162b2

To avoid immortal person-time by defining exposure groups at dose 1 based on receipt of dose 2 after baseline, all comparator vaccine recipients will begin follow-up at dose 1 for both comparisons, and the criteria for stopping follow-up will consist of the following:

- For the comparison of Ad26.COV2.S to receiving only 1 dose of BNT162b2:
 - date of first diagnosis of the AESI
 - end of the duration of the disease-specific risk period after dose 1 (specified in Table 1; up to 1 year after the reference date)
 - disenrollment from the health plan
 - administrative end of study (eg, end of available data)
 - death
 - date of receipt of a second dose of any COVID-19 vaccine (regardless of whether it is part of the primary series or is an additional dose or a booster dose)
- For the comparison of Ad26.COV2.S to receiving both doses of BNT162b2:
 - date of first diagnosis of the AESI
 - end of the duration of the disease-specific risk period after dose 1 of Ad26.COV2.S or dose
 2 of BNT162b2 (specified in Table 1; up to 1 year after the reference date)
 - disenrollment from the health plan
 - administrative end of study (eg, end of available data)
 - death
 - date of any COVID-19 vaccination that is not the same brand as the index COVID-19 vaccine
 - date of receipt of second BNT162b2 dose too early (ie., before day 17, based on CDC guidance [active comparator cohort only]) (Table C, footnote to intervals: Clinical Guidance for COVID-19 Vaccination | CDC 2022)
 - failure to receive a second dose of BNT162b2 by day 28, the recommended interval between dose 1 and 2 (21 days) plus a brief grace period for variation in real-world receipt (active comparator cohort only)
 - date of receipt of an additional or booster dose beyond the authorized primary series (ie, a second dose of COVID-19 vaccine in the Ad26.COV2.S cohort or a third dose of COVID-19 vaccine in the BNT162b2 cohort)

